**5. Inclusion/Exclusion Criteria**

Inclusion Criteria: Adult patients undergoing general anesthesia for elective cases

Exclusion Criteria: Patients under age 18; Patients not undergoing general anesthesia

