#### 4. Study Procedures

- a. Study design, including the sequence and timing of study procedures (distinguish research procedures from those that are part of routine care).

Research Procedures will be integrated into the routine part of the preoperative pre-anesthesia session. .

A member of the study team will approach the anesthesiologists who will be in the control arm of the study. None of the study team members will be in a supervisory or evaluative role to the potential anesthesiologists to be approached. Patient participants will be approached and asked if they are interested in participating. Those who are interested and eligible will undergo the research informed consent process. Patients will be divided into a **control group** and an **intervention group**. Both groups will receive the above described post-operative questionnaires with the addition of selected questions regarding their prior experience with anesthesia, and their understanding of what the anesthesiologist is responsible for. During the post-operative questionnaire they will also be asked what percentage of the signed anesthesia consent they read and if they recall anything about it. The questionnaire will be completed postoperatively, over the phone or in person, no more than 3 days after the day of the procedure.

The **control group** will have their pre-op discussion performed by an anesthesiologist in a manner commensurate with their routine for preoperative discussion. These anesthesiologists are not part of the study team. These anesthesiologists will be approached by a member of the study team and asked for permission to participate and be observed; then their patients will also be approached for participation. These anesthesiologists will be audio-recorded. Remotely, a study team member will review the audio-recording and will use a check list to assess the content communicated during the preoperative discussion. The amount of time that the discussion takes will also be recorded.

The **intervention group** will have their pre-op discussion performed by one of the two study anesthesiologists who will perform their discussion with knowledge of specific material that must be addressed prior to completion of the discussion including:

1. Description of the type of anesthesia administered
2. Description of what that type of anesthesia is (eg. what is general anesthesia?)

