**7. Study Statistics**

- a. Primary outcome variable: Recall of risks, understanding of anesthetic plan
- b. Secondary outcome variables. Anxiety relief
- c. Statistical plan: Pearson's Chi-squared statistic for categorical variables and Mann-Whitney U Tests for scaled variables.
- d. Early stopping rules.  
Study may be stopped at any time if there is a medical or public health emergency.

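### The group comparison is unadjusted and provider-based, with every type of elective surgery eligible, so any difference in surgical case mix between the groups would bias it

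*Combined protocol and SAP*

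**What the plan says.** **Who is eligible.** Section 5 (Inclusion/Exclusion Criteria) admits "Adult patients undergoing general anesthesia for elective cases". The only exclusions are "Patients under age 18; Patients not undergoing general anesthesia". Neither refers to surgical service, procedure or setting.

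**How patients reach each group.** Section 4a (Study Procedures, study design) introduces the groups with "Patients will be divided into a" control and an intervention arm, and names no mechanism. Control anesthesiologists are "asked for permission to participate and be observed; then their patients will also be approached for participation". Of these providers it says "These anesthesiologists are not part of the study team". The intervention group "will have their pre-op discussion performed by one of the two study anesthesiologists". On this text no provider serves both groups.

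**Timing.** The questionnaire is given after surgery, up to three days later (section 4a). Section 4c gives an anticipated study duration of six months and does not say whether the groups enrol at the same time.

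**Blinding and control rationale.** Section 4d speaks of patients being assigned to a group but does not say how. Section 4f asserts that having a control group removes the influence of all other variables.

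**Outcomes and analysis.** Sections 7a and 7b name recall of risks and understanding of the plan as primary, and anxiety relief as secondary. Section 7c gives Pearson's "Chi-squared statistic for categorical variables and Mann-Whitney U Tests for scaled variables", with no covariate or stratum.

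**The concern.** Group membership is tied to the provider, at least for controls, and the two sets of providers do not overlap. With every kind of elective operation eligible, nothing in the plan makes the groups alike in surgery type, and the named tests do not allow for a difference.

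The operation and early recovery fall between the discussion and the questionnaire. If pain, analgesia, length of stay or complications affect what patients remember or how anxious they feel, a difference in surgical case mix would appear as a difference in recall, understanding or anxiety. It could create an apparent benefit of the structured discussion or hide a real one.

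This error is systematic, so a larger sample does not reduce it. A larger sample makes a false conclusion more likely. Section 4f makes matters worse because it tells the reader that the problem has already been removed.

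**Working it through.** **1. Is there a figure to reproduce?** No. The supplied text gives no sample size, significance level, outcome rate or effect size. Every input below is assumed, and the results show how the mechanism scales.

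**2. Does the text supply any protection?**

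| Possible protection | What the documents state |
|---|---|
| Randomization | None stated (sections 4a, 4d) |
| Matching or restriction by service or setting | None stated (sections 4a, 5) |
| Concurrent enrolment | None stated; six-month duration only (section 4c) |
| Stratified or adjusted analysis | None; two unadjusted tests (section 7c) |
| Surgery type recorded | Cannot be determined; the questionnaire and data forms are not in the supplied text |

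**3. Size of the bias.** Take two kinds of surgery and no true effect of the discussion.

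Bias = (difference between groups in the share of one kind) × (difference in recall between the two kinds).

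Assume a 20-point recall difference and 100 patients per group. Using the largest possible variance of a proportion, SE = √(2 × 0.25 / 100) = 0.0707. The chance that a two-sided 5% test rejects is Φ(bias/SE − 1.96) + Φ(−bias/SE − 1.96).

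| Mix difference | Bias | Bias/SE | Rejection |
|---|---|---|---|
| 0.20 | 0.20 × 0.20 = 0.04 | 0.57 | 8.7% |
| 0.30 | 0.30 × 0.20 = 0.06 | 0.85 | 13.6% |
| 0.40 | 0.40 × 0.20 = 0.08 | 1.13 | 20.5% |

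**4. Check with explicit rates.** Let recall be 0.70 in one kind of surgery and 0.50 in the other, with shares of the first kind 30% in control and 70% in intervention.

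- Control: 0.3 × 0.70 + 0.7 × 0.50 = 0.56.
- Intervention: 0.7 × 0.70 + 0.3 × 0.50 = 0.64.
- Spurious difference d = 0.08.
- Pooled (null) SE at 100 per group: √(2 × 0.60 × 0.40 / 100) = 0.0693.
- Unpooled SE: √((0.56 × 0.44 + 0.64 × 0.36) / 100) = 0.0691.
- Rejection: Φ((0.08 − 1.96 × 0.0693)/0.0691) + Φ((−0.08 − 1.96 × 0.0693)/0.0691) = 21.0%, close to the 20.5% in step 3.

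**5. Range, by the formula in step 4.**

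| Recall in the two kinds | Share of first kind, control vs intervention | Spurious difference | Rejection at 50 / 100 / 200 per group |
|---|---|---|---|
| any pair tried | equal | 0 | 5% / 5% / 5% |
| 0.60, 0.50 | 40% vs 60% | 2 points | 5.5% / 5.9% / 6.9% |
| 0.70, 0.50 | 40% vs 60% | 4 points | 6.9% / 8.9% / 12.9% |
| 0.70, 0.50 | 30% vs 70% | 8 points | 12.8% / 21.0% / 37.2% |
| 0.70, 0.40 | 30% vs 70% | 12 points | 22.5% / 39.9% / 67.6% |

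The effect runs from negligible to severe depending on the inputs. Wherever the mix differs, it grows with sample size.

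**6. Effect of stratifying.** In step 4, recall within the first kind of surgery is 0.70 in both groups, and within the second it is 0.50 in both. Each within-stratum difference is 0, so any weighted average of them is 0.

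**The case against.** **The route into the intervention group is not given.** Section 4a says who holds the intervention discussion, not how patients come to those two anesthesiologists. Sections 4a and 4d speak of patients being divided and assigned. A reader might infer that each group simply follows an anesthesiologist's operating list and so must differ in surgery type. The documents do not show this: they mention no lists, and if the study pair see patients across services the mix could be similar. This part of the objection stands. What remains is that the control route does run through the provider, and no stated mechanism makes the groups comparable.

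**The causal link and the figures are assumed.** This also stands. Nothing in the documents shows that surgery type affects recall or anxiety, and the mildest case in the table barely moves the error rate.

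**Surgery type may be recorded.** A reader might infer that it is not, because no supplied section mentions it. The questionnaire and data forms are not in the text, so this cannot be settled either way.

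**Enrolment may be concurrent.** A reader might infer that the groups enrol one after the other. Nothing suggests that; the text only fails to require the same weeks.

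**Broad eligibility is legitimate.** It is, and it supports generalisability. The difficulty is broad eligibility combined with provider-based groups and an unadjusted analysis.

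**Provider confounding would remain.** It would: two study anesthesiologists would still be compared with different, consenting colleagues. Case mix is an additional problem that can be reduced separately.

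**Conclusion.** The point holds in conditional form. Followed as written, the plan makes an unadjusted comparison of groups that are not stated to be randomized, are defined at least partly by provider, and are drawn from all elective general-anesthesia surgery. If case mix differs between the providers' patients and also affects the outcomes, the result is biased, and section 4f's assurance does not hold.

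The documents do not establish that case mix will differ, and they do not allow the bias to be estimated. The 4 to 8 points of bias and the roughly 9% to 21% false-positive rates at 100 per group illustrate assumed inputs and should not be read as predictions for this trial. The case for change rests on the missing protection and the low cost of adding it.

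**What to change.** 1. Record surgical service and day-case or inpatient setting for every patient. Fix the coding before enrolment, because section 8b de-identifies data at entry and the information may be hard to recover later.
2. State in section 4a how patients come to each group. Enrol both groups over the same calendar weeks and, where feasible, from the same services. Same-service recruitment is a trade-off: it improves comparability but may reduce the number of willing control anesthesiologists and narrows generalisability.
3. In section 7c, make the primary comparison stratified by broad service and setting categories: Cochran-Mantel-Haenszel for categorical outcomes and van Elteren for scaled ones. A regression model with these as covariates is an alternative. Define the categories in advance and keep them coarse, since a stratum containing only one group contributes nothing to a stratified test.
4. Replace the sentence in section 4f with a statement that the control group gives a reference for usual discussion and that residual confounding, including by provider, remains.

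The cost is two data fields, slightly more analysis, a few lines of text, and some loss of information if strata are sparse. These changes reduce confounding by case mix. They do not separate the effect of the structured discussion from the effect of who delivers it.

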**6. Drugs/ Substances/ Devices**

a. The rationale for choosing the drug and dose or for choosing the device to be used. N/A

b. Justification and safety information if FDA approved drugs will be administered for non-FDA approved indications or if doses or routes of administration or participant populations are changed. N/A

Justification and safety information if non-FDA approved drugs without an IND will be administered. N/

**7. Study Statistics**

- a. Primary outcome variable: Recall of risks, understanding of anesthetic plan
- b. Secondary outcome variables. Anxiety relief
- c. Statistical plan: Pearson's Chi-squared statistic for categorical variables and Mann-Whitney U Tests for scaled variables.
- d. Early stopping rules.  
Study may be stopped at any time if there is a medical or public health emergency.

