### 2. Objectives (include all primary and secondary objectives)

Primary objectives: - Determine the percentage of people with an accurate knowledge of what general anesthesia is. - Define the public's perception of the role of the anesthesiologist in the operating room. - Help patients and the public to better understand the risks and safety aspects of anesthesiology Secondary objectives - Improve anesthesiologist-patient relations. - Decrease the likelihood of malpractice suits. - Improve the professional standing of anesthesiology. - Patients will know that the anesthesiologist is not a person who just puts them to sleep and then abandons them. - Decrease fear of the anesthesia experience. - Decrease fear of the anesthesia face-mask. - Improve medical student recruitment into anesthesiology as a career choice.

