3. The expected anesthesia related procedures to be performed and the possibility of additional procedures performed if necessary.
4. anesthesia risk
5. Intraoperative communication with the rest of the operating room team
6. Communication to the patient that everything done will be in the interest of safety
7. Plans for pain and nausea control
8. An offer to address any additional questions that the patient may have

These anesthesiologists will also be -audio-recorded. Remotely, a study team member will review the audio-recording and will use a check list to assess the content communicated during the preoperative discussion. The amount of time that the discussion takes will also be recorded.

A comparison of the questionnaire results between the control and intervention groups will be made, and data will be statistically analyzed at the end of the study and data entry period.

- b. If your study involves data/biospecimens from participants enrolled under other research studies with a written consent or under a waiver of consent, please list the IRB application numbers for those studies. Please note: Certificate of Confidentiality (CoC) protections applied to the data in source studies funded by NIH or CDC will extend to this new study if the funding was active in 2016. If this situation applies, Section 36, question 4 in the application will need to be answered “Yes” and “Hopkins Faculty” should be selected in question 7. No other documents are required. N/A
- c. Study duration and number of study visits required of research participants. Study duration is anticipated to be 6 months and does not require any follow up visits from the research participants.
- d. Blinding, including justification for blinding or not blinding the trial, if applicable. Patients will be blinded to the group that they are assigned to. (control vs. intervention).
- e. Justification of why participants will not receive routine care or will have current therapy stopped. This study does not interrupt routine care for patients.
- f. Justification for inclusion of a placebo or non-treatment group.  
A control group is used to show the standard without the intervention and will be used to compare any similarities or differences to outcomes in the intervention group. Having a **control group** eliminates the potential impact of all other variables.
- g. Definition of treatment failure or participant removal criteria.  

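### Two primary constructs are to be tested with no multiplicity control and no rule for a split result, so either one could be claimed as the positive primary finding

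*Combined protocol and SAP*

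**What the plan says.** Section 7a reads "Primary outcome variable: Recall of risks, understanding of anesthetic plan". The label is singular, but two things are listed, and neither a ranking nor a combined score is given. Section 7b adds "Secondary outcome variables. Anxiety relief". The whole statistical plan in section 7c is "Pearson's Chi-squared statistic for categorical variables and Mann-Whitney U Tests for scaled variables". It does not say which type of variable either primary construct is.

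Section 4a says that "A comparison of the questionnaire results between the control and intervention groups will be made", with analysis at the end of the study. The only stopping provision, in section 7d, is "Study may be stopped at any time if there is a medical or public health emergency"; it is not statistical and adds no tests.

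The primary objectives in section 2 do not settle the matter. One of them, "Help patients and the public to better understand the risks and safety aspects of anesthesiology", is close to recall of risks. None names understanding of the anesthetic plan or ranks it against recall. The supplied text contains no significance level, sidedness, power, sample size, testing order or success rule.

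**The concern.** A split result, with one construct significant and the other not, is easy to foresee. The plan does not say whether that makes the study positive, so the choice could be made once the results are known. The error rate of the primary claim depends on that choice.

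Three readings are open:

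- Either construct suffices. The false-positive chance then exceeds the per-test level.
- Both must succeed. There is no inflation, but some loss of power.
- One combined score is meant. There is no inflation, but no combination is defined in the text.

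The abstract in section 1 expects a favorable answer to influence practice nationally, so the basis for calling the result positive should be fixed in advance.

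**Working it through.** The plan gives no error rate or power figure to reproduce, so everything below is conditional.

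**Inputs from the plan.** Two primary constructs (section 7a); tests chosen by variable type with no adjustment (section 7c); one analysis at the end (section 4a).

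**Assumptions, none stated in the plan.** Two-sided 5% per test, each test truly holding 5%; one test per construct; no true effect on either; correlation between the test statistics from 0 to 0.99. For correlated tests the statistics are taken as jointly normal.

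**Step 1: either construct suffices.** If independent, 1 − (1 − 0.05)² = 1 − 0.9025 = 0.0975. Without any assumption on dependence, the bound is 0.05 + 0.05 = 0.10. For correlated statistics, the chance is 1 − P(|Z₁| < 1.960 and |Z₂| < 1.960).

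**Step 2: both required.** The chance that both are falsely significant is 0.05 + 0.05 minus the step 1 figure. It cannot exceed 5%.

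**Step 3: Holm.** With no true effects, an error needs at least one p-value at or below 0.025, for which the critical value is 2.241. If independent, 1 − 0.975² = 0.0494.

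| Correlation | Either suffices | Both required | Holm |
|---|---|---|---|
| 0 | 9.75% | 0.25% | 4.94% |
| 0.5 | 9.07% | 0.93% | 4.65% |
| 0.9 | 7.04% | 2.96% | 3.62% |
| 0.99 | 5.66% | 4.34% | 2.86% |

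**Step 4: sensitivity to the assumptions.** With independent tests at 1% each, the either-suffices figure is 1 − 0.99² = 1.99%; at 10% each it is 1 − 0.90² = 19.0%. With two tests per construct, four in all, at 5% each, it is 1 − 0.95⁴ = 18.5% if independent.

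**Step 5: power cost of Holm.** Assume 80% power per outcome at two-sided 0.05, so the expected test statistic is 1.960 + 0.842 = 2.802.

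- An outcome that must pass at 0.025 has power Φ(2.802 − 2.241) = Φ(0.561) = 0.712. Restoring 80% would need ((0.842 + 2.241)/(0.842 + 1.960))² = 1.21 times the patients.
- If both effects are real and the tests independent, power per outcome is 0.712 + (0.800 − 0.712) × 0.712 = 0.775. By simulation of 4 million pairs it is 0.765 at correlation 0.5, 0.751 at 0.9 and 0.731 at 0.99.
- For comparison, the chance that both are significant at 0.05 is 0.80² = 0.640 at correlation 0, about 0.75 at 0.9 and about 0.78 at 0.99.

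**The case against.** The strongest reply is that the 9.75% figure needs conditions that the plan does not state: a 5% level, an either-suffices rule, one test per construct and zero correlation. The singular label in section 7a leans toward one endpoint, and two of the three readings carry no inflation. Both constructs come from one questionnaire in the same patients, so positive correlation is likely and the true figure would probably be below 9.75%. This stands, and the figure is offered only as an illustration.

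Second, the more basic gap may be endpoint definition. How each construct is scored, and from how many items, is not given, and step 4 shows that the number of tests matters. Section 4a refers to questionnaires described above it, and no such description is in the supplied text, so scoring may exist in an instrument not seen here. That also stands, and it is why the fix begins with one score per construct. Scoring alone, however, would not settle what a split result means.

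Third, the two constructs could defensibly be reported separately and in full. That is reasonable for description, but it still leaves open which result supports the primary claim.

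Two stronger inferences are tempting. A reader might conclude that this trial's false-positive rate is 9.75%; the documents do not support that, because they fix neither the level nor the success rule. A reader might also conclude that adjustment would bring the trial's true error to 5%. It would not: section 4a gives the intervention discussions to two study anesthesiologists and the control discussions to others, and a multiplicity rule does nothing about that.

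**Conclusion.** The point holds as an unresolved decision rule, not as a demonstrated error rate. The omission is plain across the supplied text. If the plan is followed literally, two separate unadjusted tests are run and either could be presented as the primary success. The excess over an assumed 5% is at most 5 percentage points under any dependence with one test per construct, and it shrinks as the correlation rises. It is zero if both must succeed or if one combined score is intended. Because the remedy is cheap and can only be prespecified before data are seen, the change should be made. Confidence is medium, since the size depends on a choice that the plan leaves unwritten.

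**What to change.** Before any data are seen:

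- In section 7a, define one score for recall of risks and one for understanding of the anesthetic plan, each with its variable type so that the test in section 7c follows.
- In section 7c, state that the two primary scores are tested by Holm's procedure at a two-sided familywise 5%: the smaller p-value is compared with 0.025 and, if it passes, the larger with 0.05. A fixed testing order, or a rule that both must succeed, is also acceptable if it is what the investigators intend and is written down now.
- Keep anxiety relief as the secondary outcome, outside the primary family. Label the other between-group questionnaire comparisons exploratory; they need not be dropped or reduced to description.

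The drafting cost is a few sentences plus the work of scoring each construct. The statistical cost under Holm, with 80% per outcome at 0.05 assumed, is power of about 71% for an outcome that must pass at 0.025 (about 21% more patients would restore 80%), or about 73% to 78% per outcome when both effects are real. A fixed order costs the first outcome nothing; when both effects are real, the second then succeeds with probability about 64% to 78%, the same as the chance that both succeed under a both-required rule. The tie between arm and anesthesiologist needs separate attention.

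### Every intervention discussion comes from two study anesthesiologists and no randomization is described, so the Section 7c tests cannot attribute a difference to the structured discussion, and Section 4f says otherwise

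*Combined protocol and SAP*

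**What the plan says.** Section 4a describes the two arms. The intervention discussion is "performed by one of the two study anesthesiologists", who must cover eight listed items. The control discussion follows each anesthesiologist's own routine, and the text adds: "These anesthesiologists are not part of the study team". No section has an anesthesiologist working in both arms.

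On how patients reach an arm, Section 4a says "Patients will be divided into a" control group and an intervention group. For the control arm, anesthesiologists give permission first, "then their patients will also be approached for participation". Section 4d says "Patients will be blinded to the group that they are assigned to", which implies some assignment but gives no mechanism. The sections available describe no randomization.

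Section 4f justifies the control group on the ground that it "eliminates the potential impact of all other variables". The whole analysis in Section 7c is Pearson's "Chi-squared statistic for categorical variables and Mann-Whitney U Tests for scaled variables", with no term for provider, no allowance for clustering and no use of patient characteristics. The post-operative questionnaire does include "selected questions regarding their prior experience with anesthesia", and the discussions in both arms are audio-recorded, timed and scored on a checklist, but no role in the comparison is stated for any of these.

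**The concern.** The study wants to learn whether a structured discussion improves recall and understanding. The arms differ in at least two other ways.

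- **Provider.** The intervention patients are seen by two members of the study team, the control patients by other people. Skill, motivation and investigator status move with the arm.
- **Patients.** With no described allocation method, and with control patients reached through their anesthesiologist, the two groups may differ in ways related to recall, such as earlier anesthesia.

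Neither test in 7c addresses either difference, and 4f tells the reader that both have been removed. The abstract foresees, conditionally, consequences for practice across the country. A conclusion of that scope would rest on two intervention providers, and enrolling more patients would not change that.

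**Working it through.** **Structure.** Intervention providers are two study anesthesiologists; control providers are all outside the study team. The sets do not overlap, so a provider term in a model cannot be separated from the arm term. This needs no numbers. Randomizing patients would deal with patient mix but leave provider and arm confounded.

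**Illustration of size.** The documents give no sample size, number of control anesthesiologists, intraclass correlation (ICC) or patient mix, so there is no figure to reproduce. Assumed throughout: two-sided 5% test, 50% outcome rate, n = 50 or 100 patients per arm, and, unless stated, k = 8 control providers.

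*(a) Claims beyond these providers.* Design effect per arm = 1 + (m − 1) × ICC, with m = n/2 (intervention) or n/k (control). Type I error = 2 × [1 − Φ(1.96/√(mean design effect))].

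Example, n = 50, ICC 0.05: intervention 1 + 24 × 0.05 = 2.20; control 1 + 5.25 × 0.05 = 1.2625; mean 1.731; 1.96/√1.731 = 1.49; type I error 13.6%.

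| ICC, both arms | n = 50: formula (simulated) | n = 100: formula (simulated) |
|---|---|---|
| 0 | 5% (5.6% to 5.7% for both n) | 5% |
| 0.01 | 6.7% (7.6%) | 8.6% (9.4%) |
| 0.05 | 13.6% (15.2%) | 21.6% (23.1%) |
| 0.10 | 21.2% (23.0%) | 32.9% (35.0%) |

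Simulated values are for the chi-squared test on beta-binomial data. Across 4 to 12 control providers and ICC 0.01 to 0.10, simulation gives 7.4% to 25.9% at n = 50 and 9.1% to 38.3% at n = 100. If every control patient had a different anesthesiologist, the formula would still give 12.1% and 18.9% at ICC 0.05. A separate simulation with 10 control providers and ICC 0.05 gives Mann-Whitney 13.2% (n = 50) and 20.6% (n = 100), against 14.9% and 22.4% for chi-squared.

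*(b) If the required items make the two study providers more alike.* With control ICC 0.05 and intervention ICC 0 to 0.01, the formula gives 6.5% to 8.0% at n = 50 (simulated 7.4% to 8.7%) and 8.4% to 11.3% at n = 100 (simulated 9.3% to 12.5%).

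*(c) Floor on precision.* The two intervention providers alone add a 95% half-width of 1.96 × √(ICC × 0.25/2), however many patients are enrolled: 6.9 percentage points at ICC 0.01, 15.5 at 0.05, none at 0.

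*(d) Patient mix, with identical providers and no effect of the discussion.* Suppose a trait is present in 60% of one arm and 40% of the other.

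- Outcome rates 60% with the trait and 40% without: 0.6 × 0.6 + 0.4 × 0.4 = 52% against 0.4 × 0.6 + 0.6 × 0.4 = 48%, a spurious 4 points. The chi-squared test rejects in 7.7% (n = 50) and 9.5% (n = 100).
- Outcome rates 65% and 35%: 53% against 47%, a spurious 6 points. It rejects in 10.1% and 14.8%.

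**The case against.** The strongest reply is that 7c names tests and claims no attribution. Section 4a promises a comparison of questionnaire results between two groups, and for that comparison the tests are valid. The fault then lies in the design and in 4f rather than in the choice of test. This is fair as to where most of the repair belongs. But 7c is the whole analysis plan, and with 4f beside it a reader would take a significant result as the effect of the discussion.

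The type I error argument applies only to claims beyond these providers, and every input is assumed. If the study providers behave alike, the inflation is modest. That stands, so the conclusion does not rest on those figures. Confounding remains even at ICC 0 if the two providers differ on average from the controls.

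A cluster analysis with two intervention clusters also performs poorly. That stands too, and it is a reason to narrow the claim rather than rely on a better test.

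Finally, 4d speaks of assignment, so an allocation method may exist. The point is therefore put as not described, and patient imbalance as possible rather than shown.

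**Conclusion.** The concern holds and must be fixed. On the plan's own description, provider and arm are completely confounded, no allocation method is given, and 7c handles neither provider nor patient mix. The 4f sentence claims a property that the design lacks. The planned tests can show that patients of the two study anesthesiologists answered differently from patients of the participating control anesthesiologists. They cannot by themselves attribute the difference to the structured discussion, and no reanalysis can separate the two.

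The added uncertainty for wider claims ranges from none at ICC 0 to a type I error of about a third at ICC 0.10 with 100 patients per arm and 8 control providers. All of those inputs are assumptions.

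**What to change.** 1. **Section 4f and 4a.** Replace the 4f sentence with a statement that the control group does not remove differences between providers or, without randomization, between patients. State in 4a how patients are divided.
2. **Section 7c.** State that the patient-level tests compare patients of the two study anesthesiologists with patients of the participating control anesthesiologists, and do not by themselves attribute a difference to the structured discussion.
3. **Data and tables.** Keep a coded provider identifier, secured before the de-identification at data entry in Section 8b. Report outcomes and checklist content by anesthesiologist, and patient characteristics by arm, including prior anesthesia experience.
4. **Only for claims beyond these providers.** Use an analysis with anesthesiologist as the cluster and small-sample degrees of freedom. Say that two intervention clusters make it fragile and that it does not remove the confounding.
5. **Optional, if the design is still open.** Have more anesthesiologists give the structured discussion. With 8 instead of 2 (ICC 0.05, 8 control providers), approximate type I error falls from 13.6% to 8.1% at 50 per arm and from 21.6% to 11.8% at 100, and the half-width in (c) from 15.5 to 7.7 points. Unless anesthesiologists are allocated to arm at random, this reduces dependence on two people but leaves the confounding.

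**Cost.** Items 1 to 3 need wording, a provider code (the documents do not say whether one is kept) and descriptive tables. The conclusion becomes narrower, and results by provider may identify the two study anesthesiologists even when coded.

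Item 4 costs power. With 8 control providers, ICC 0.05 and rates of 50% against 70% (all assumed), a pooled t-test on provider means has power 12% at 50 per arm and 21% at 100, with size about 2%. A Welch version has power 29% and 35%, but size 7% to 8%. The pooled test is conservative even at ICC 0 (size about 1%), so part of its loss comes from the test and the two clusters rather than from correlation.

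Item 5 costs recruiting and training more anesthesiologists.
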